Primary objective: In relation to the participants' chronotype, the objective will be to evaluate the effect of irregular working hours on the quality of sleep, on the circadian rhythm of activity levels and on motor control, to identify the type of shift with less impact on the state of health of the hospital staff.

Secondary objective: Evaluations of heart rate variability, circadian rhythm of activity levels, sleep quality and motor control for the definition of alterations related to the effect of the shift.

[figure not shown]
STUDY DESIGN

The project involves the recruitment of nursing staff of the IRCCS Galeazzi Orthopedic Institute of Milan, which is subjected to three types of shift:

- GROUP 1: total duration 5 days, 24-hour shifts;
- GROUP 2: total duration 10 days, 24-hour shifts;
- GROUP 3: diurnal shifts only (control).

The experimental design is schematized as shown in Figure 1.

Figure1: Experimental design.

Upon recruitment, all participants will undergo to the following evaluations (see Figure 2):

- Questionnaire Horne-Ostberg Morningness-Eveningness Questionnaire (MEQ) for the determination of the chronotype (Horne JA, Ostberg O. 1976);
- International Physical Activity Questionnaire (IPAQ) for the assessment of the level of physical activity;
- QRISK2-2017 questionnaire for cardiovascular risk assessment (Hippisley-Cox J, 2010; Hippisley-Cox J, 2008).

All the questionnaires are validated in Italian except the QRISK2-2017, which will be administered by medical personnel.

During the entire duration of the shift, all participants will be subjected to actigraphic monitoring to assess the quality of sleep and circadian rhythm activity-rest. Monitoring will start from the first day of the shift and will continue for 10 consecutive days for all three groups. During the entire duration of the monitoring the participants will have to fill in a diary on which they will note the hours of alarm, of falling asleep and any intervals of time during which the actigraph will be removed.

At the beginning, after 5, 7 and 8 days of shift for GROUP 3, GROUP 2 and GROUP 1, respectively, participants will undergo to:

- Evaluations of the motor control and level of neuromuscular activation of the finger flexor muscles;
- Heart rate variability analysis by monitoring heart rate;
- Profile of Mood States (POMS) questionnaire for the determination of the mood profile.

Figure 2

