The population consists of about 120 potential participants recruited within the nursing staff belonging to the Galeazzi Orthopedic Institute, of which 60 potentially belong to GROUP 1, 20 to GROUP 2 and 40 to GROUP 3.

Inclusion criteria: Both sexes who have a continuity of shift in the specific group of at least one year will be included in the study.

Exclusion criteria: All participants will be excluded from the project with documented presence of cardiovascular, endocrine and metabolic diseases and / or pharmacological therapies in place that can modulate the heart rate and the quality of sleep. Participants with self-declaration of pregnancy status will also be excluded from the study.

Participation and completion of the study: The participant is considered enrolled in the study when providing written informed consent. No study procedure will be initiated before the Informed Consent is signed. Participation in the study may end before its completion for the reasons described in the dedicated section. The whole study ends when the last subject has completed the study or has been withdrawn from the study.

Interruption of the participation to the study: Participants have the possibility to withdraw from the project at any time. In the latter case, personal data will be completely erased while the scientific data collected until the time of the possible withdrawal, will be used anonymously for purely scientific purposes. Participants must promptly notify the inability to continue the study.

The study does not provide for follow-up but some samples or evaluations could be lost. Any participants lost during the study will not be replaced.

CLINICAL EVALUATIONS

Evaluation of the chronotype: the administration of the MEQ questionnaire will allow, on the basis of the scores obtained, dividing the sample into the three corresponding chronotypes (M-Types, N-Types to E-Types). Morningness/eveningness can have a major impact on the well being of the individual through sleep-related influences, as it interferes with normal daily functions.

Assessment of the level of physical activity: the IPAQ questionnaire includes 4 sets of questions that investigate four different aspects of the level of physical activity in relation to health.

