and end of sleep; (iii) Sleep Latency (SL), period of time between bed and sleep; (iv) Movement and Fragmentation Index (MFI), percentage of time spent moving indicative of the fragmentation of sleep and (v) Immobile Time (IT) total time spent without movement, between sleep from start to sleep.

To determine the circadian rhythm in the three chronotypes, the data relating to the activity provided by the actigraph would be analyzed using the single Cosinor method, which identifies and evaluates the cosinusoidal mathematical function that it is better suited to data as a function of time. The function defines three parameters that are characteristic of each rhythm: MESOR (Midline Estimating Statistic of Rhythm), amplitude and acrophase. The rhythmic parameters of the activity levels will be elaborated with the Cosinor Population, in order to evaluate the rhythmic characteristics of the levels of activity for each chronotype.

EVALUATION AND REGISTRATION OF ADVERSE REACTIONS

Safety and evaluation of adverse reactions in relation to the techniques used Participating subjects will be closely monitored for possible side effects.

Criteria for suspension of the study: Suspension from the study is planned based on the doctor's assessment in the cases specified above. Participants will be informed in the consensus session that participation in the study can be interrupted at any time.

Data collection for retired participants: Even if participants can withdraw from the study, undesirable effects will be recorded.

Risk/Benefits Report: As no invasive measures are planned within the study, participants will not be exposed to particular risks. The results will provide useful information to be able to reason on any revaluations of the shift system by making any changes.

STATISTICAL ANALYSIS

The sample size was calculated (Sigmaplot mod software 12.5) on the basis of the results of a previous study (Martin et al., 2015), which is structured with an experimental design similar to that proposed in the present project. In consideration of the main objective of the project, the sleep efficiency was identified as the main outcome. An analysis of variance (ANOVA) model, a minimum detectable change percentage of 5%, a residual standard deviation of 6.9 and a number of groups equal to 3 were considered for sample size quantification. On these basis, a number of 37 participants would guarantee a statistical power > 0.80 with an α value <0.05.

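### The power statement does not say whether 37 is a total or a group size: as a total, power is about 0.32 to 0.41; as a shift-group size, 37 exceeds the 20 potential staff in Group 2

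*Combined protocol and SAP*

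**What the plan says.** The only sample-size statement is in the Statistical Analysis section. It names sleep efficiency as the main outcome and an ANOVA as the model, with "a minimum detectable change percentage of 5%, a residual standard deviation of 6.9 and a number of groups equal to 3", and concludes that "a number of 37 participants would guarantee a statistical power > 0.80 with an α value <0.05". It does not give the unit of 37, the identity of the three groups, the pattern of group means, or whether the 5% is absolute or relative.

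Other sections bear on how to read it:

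- **Available staff (population paragraph under Study Design).** "The population consists of about 120 potential participants", "of which 60 potentially belong to GROUP 1, 20 to GROUP 2 and 40 to GROUP 3".
- **Inclusion criterion.** Participants need "continuity of shift in the specific group of at least one year".
- **Losses.** "Any participants lost during the study will not be replaced".
- **Primary objective (Aims).** The purpose, in relation to chronotype, is "to identify the type of shift with less impact on the state of health of the hospital staff".
- **Chronotype (Clinical Evaluations).** The questionnaire serves for "dividing the sample into the three corresponding chronotypes". No expected number per chronotype is given.
- **Sleep efficiency (Clinical Evaluations).** It is itself a percentage, so a 5% change can be read as 5 points or as one twentieth of the mean.

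**The concern.** Read plainly, the sentence says that 37 people in the whole study are enough. A team working to that total would have about 12 per group, and the stated inputs do not give 0.80 power at that size. Read as a group size, the figure conflicts with the protocol's own staffing count if the groups are shifts, because Group 2 cannot supply 37 people.

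This is the only basis on which an ethics committee or a reader can judge whether the study can answer its main question. That question is about which shift has less impact, so the shift reading cannot be set aside. If the power is overstated, a null result on sleep efficiency could be taken as evidence that the shifts are alike, when the study had limited ability to show a difference involving Group 2.

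**Working it through.** **Inputs from the protocol.** k = 3 groups, SD 6.9, change of 5%, alpha 0.05, n = 37, pool of 60/20/40.

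**Assumptions, because the protocol is silent.** The 5% is 5 points between the extreme means. Each person contributes one value, with SD 6.9. Two patterns of means are used: third mean midway (−2.5, 0, 2.5), and one group different (0, 0, 5).

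**Method.** Overall F test with the noncentral F distribution. With m̄ the weighted grand mean, λ = Σ nᵢ(μᵢ − m̄)² / 6.9², with 2 and N − 3 degrees of freedom; 6.9² = 47.61. For equal groups, Σ(μᵢ − m̄)² is 12.5 (midway) or 16.67 (one group differs).

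**Step 1: can the plan's figure be reproduced?**

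| Reading of 37 | Pattern | λ | Power |
|---|---|---|---|
| Per group (N = 111) | midway | 37 × 12.5 / 47.61 = 9.71 | 0.792 |
| Per group (N = 111) | one differs | 37 × 16.67 / 47.61 = 12.95 | 0.899 |
| Total (12.33 per group) | midway | 12.33 × 12.5 / 47.61 = 3.24 | 0.318 |
| Total (12.33 per group) | one differs | 12.33 × 16.67 / 47.61 = 4.32 | 0.411 |

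Whole-number splits of 37 give 0.311 to 0.322 (midway) and 0.406 to 0.420 (one differs). In the midway pattern, 38 per group reaches 0.803, so 37 per group is one person short of an exact match. A chi-square approximation gives 0.803 at 37. Per group is therefore the likely origin of the figure; 3 × 37 = 111 also fits a pool of about 120.

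**Step 2: relative 5%.** If mean sleep efficiency is 80 to 90% (an assumption), the difference is 4.0 to 4.5 points. Power is then 0.22 to 0.34 for 37 in total and 0.59 to 0.82 for 37 per group, over both patterns.

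**Step 3: repeated measures.** If 37 people were each measured in all three conditions, with 2 and 72 degrees of freedom, power would be 0.786 (midway). The inclusion criterion ties each person to one shift group for at least a year, and chronotypes are also different people, so this model does not fit the design.

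**Step 4: the staff available, if the groups are shifts.** Group 2 is 37 − 20 = 17 short. Enrolling all 60/20/40 with a 5-point difference gives:

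| Pattern | λ | Power | Difference detectable at 0.80 |
|---|---|---|---|
| Groups 1 and 3 extreme, Group 2 midway | 12.69 | 0.893 | 4.41 |
| Group 1 alone differs | 15.75 | 0.949 | 3.96 |
| Group 3 alone differs | 14.00 | 0.921 | 4.20 |
| Groups 1 and 2 extreme, Group 3 midway | 8.75 | 0.747 | 5.31 |
| Group 2 alone differs | 8.75 | 0.747 | 5.31 |
| Groups 2 and 3 extreme, Group 1 midway | 7.44 | 0.672 | 5.76 |

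For example, with Group 2 alone different, λ = 25 × (20 × 100 / 120) / 47.61 = 8.75. These are full-uptake figures, before exclusions, refusals and losses.

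**The case against.** There are four serious points on the other side.

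1. **Other patterns of means.** The protocol states none. If 5 points is the gap between neighbouring groups (0, 5, 10), 37 in total gives 0.88, and the claim of more than 0.80 would be true. But the extreme difference is then 10 points, not the stated 5% change, and a total of 31 would be enough, so this does not explain the figure of 37. What stands is that the total reading fails under a declared assumption, not under every conceivable one.
2. **Averaging over nights.** Actigraphy runs for 10 days. If 6.9 were a per-night SD and 10 nights were averaged, 37 in total would give 0.84/0.93 (midway/one differs) at a within-person correlation of 0.2, 0.72/0.84 at 0.3 and 0.54/0.67 at 0.5. Nothing in the protocol says 6.9 is per night, and no such correlation is stated. This is a reason for the sponsor to say what the SD is.
3. **Per group is an inference.** Exact power at 37 per group is 0.792 in the midway pattern, just under the claim. This stands, so the restatement must wait for the software inputs to be confirmed.
4. **No target of 37 is set for Group 2, and the groups need not be equal.** This is true, and in half of the patterns the full pool gives 0.89 to 0.95. It does not rescue the guarantee, which would have to hold whichever group differs. If the groups are chronotypes, the Group 2 shortfall does not apply, but 37 in each then cannot be checked.

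**Conclusion.** The concern holds. Two parts need no assumption about the effect: the unit of 37 is missing, and 37 per shift group cannot be reached with 20 potential staff in Group 2.

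The power values rest on a one-way overall F test, SD 6.9 for a single value per person, and 5 points as the largest difference between means. On that basis 37 in total gives 0.32 to 0.41, or 0.22 to 0.34 if 5% is relative to a mean of 80 to 90%. The full staff pool gives 0.67 to 0.95, and is below 0.80 in the three patterns where Group 2 is an extreme with the third mean midway or differs alone. For a shift comparison, the guarantee is not met on either reading of 37. For a chronotype comparison, it cannot be assessed from the protocol.

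This must be corrected, because it is the only power claim for the main outcome.

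**What to change.** Ask the sponsor to retrieve the software inputs and rewrite the sample-size paragraph so that it states:

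- **The unit of 37.** If the inputs confirm it, say that 37 is per group, about 111 in total, with power about 0.80, so that it cannot be read as the total.
- **The effect and the SD.** Say whether 5% is absolute or relative, which pattern of means was used, and what the SD of 6.9 refers to.
- **The three groups.** Say whether they are shifts or chronotypes.
- **If shifts.** Replace the guarantee with the power the 60/20/40 pool can give. At full uptake and 5 points this is 0.89 with Groups 1 and 3 as extremes, 0.95 with Group 1 alone different and 0.92 with Group 3 alone different, but 0.67 to 0.75 in the three Group 2 patterns. Add that power falls with lower uptake.
- **If chronotypes.** Give the number expected in each and the power with those numbers.

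The cost is protocol wording, plus a recalculation if the confirmed inputs differ from the assumptions used here. The stated power becomes less favourable. No extra enrolment is proposed.

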A Shapiro-Wilk test will be applied to check the normal distribution of the sample.

A linear mixed ANOVA with Bonferroni correction, with a Tukey-Kramer post-hoc test will be applied to estimate the effects of the work shift on the different chronotypes (quality of sleep, circadian rhythms of activity levels, motor control, cardiovascular risk and mood profile). In the opposite case, the Box and Cox method will be used as non-parametric approaches.

MONITORING, VERIFICATION, STUDY INSPECTION

Study insurance and monitoring: Given the non-invasive nature of the procedures envisaged by the study, monitoring activities and the stipulation of an ad hoc insurance policy are not considered necessary.

Verification and inspection: The main investigator will allow monitoring, verification and inspections related to the study by the Ethics Committee, the promoter, the bodies required by law, the quality assurance commissions of all documents. The main investigator will ensure the possibility of inspections if applicable to the structures connected to the study. Participation as a principal investigator in this study implies acceptance of a possible inspection by the competent authorities and university offices for quality assurance.

ADHERENCE TO ETHICAL, REGULATORY AND ADMINISTRATIVE FACTORS

Ethics Committee: This study will be conducted according to the ethical principles of the Helsinki Declaration and the indications of good clinical practice, in compliance with regulatory requirements and legal obligations. By subscribing this protocol, the experimenters agree to comply with these requirements and to conduct the study diligently and efficiently and in accordance with this protocol.

This protocol and any amendments will be submitted to the EC in accordance with the legal obligations for formal approval of the study. The EC decision on the conduct of the study will be written to the coordinator and a copy of this decision will be provided to the promoter's representative before the start of the study.

Written informed consent is required for all participants.

Information to the participants and their consent: Complete information on the study and details of the protocol must be discussed with each potential subject, and an informed written consent must be obtained for all participants before carrying out any procedure or registration related to the study.

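### The power above 0.80 said to be guaranteed by 37 participants does not cover chronotype-specific shift effects, and is not assured for the overall shift comparison at the attainable group sizes

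*Combined protocol and SAP*

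**What the plan says.** All references are to the combined protocol and SAP.

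- **Main aim, as given in the AIMS section:** "In relation to the participants' chronotype, the objective will be to evaluate the effect of irregular working hours on the quality of sleep". The same sentence also seeks the shift type that affects staff health least.
- **STUDY DESIGN:** the nursing staff is one "which is subjected to three types of shift".
- **CLINICAL EVALUATIONS, chronotype:** the questionnaire scores are used for "dividing the sample into the three corresponding chronotypes".
- **STATISTICAL ANALYSIS, sample size:** "In consideration of the main objective of the project, the sleep efficiency was identified as the main outcome". The inputs are an ANOVA, a minimum detectable change of 5%, a residual SD of 6.9 and alpha 0.05, and "a number of groups equal to 3 were considered for sample size quantification". The conclusion is that "a number of 37 participants would guarantee a statistical power > 0.80".
- **STATISTICAL ANALYSIS, model:** a linear mixed ANOVA "will be applied to estimate the effects of the work shift on the different chronotypes".
- **Study population text, before CLINICAL EVALUATIONS:** of about 120 potential participants, "60 potentially belong to GROUP 1, 20 to GROUP 2 and 40 to GROUP 3". Lost participants are not replaced.

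The sample size paragraph does not say which three groups are meant, whether 37 is a total or a number per group, whether 5% is absolute or relative, or whether 6.9 is a per-person or a one-night SD.

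**The concern.** The power statement is attached to an objective that it does not address. Both the objective and the planned model ask how shift effects behave across chronotypes. The calculation has one grouping with three levels and no second factor, interaction, within-chronotype contrast or chronotype distribution. Whether the three groups are shifts or chronotypes, the chronotype-specific question is not sized.

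There is a second difficulty for the overall shift comparison. If 37 is a number per shift group, Group 2 cannot supply it.

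The protocol expects its results to inform changes to the shift system. A non-significant shift effect in a handful of nurses of one chronotype, read against a guaranteed power above 0.80, could be taken to show that a schedule is harmless for them when the study was never sized to show that.

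**Working it through.** **Inputs from the documents:** difference 5, SD 6.9 (6.9² = 47.61), 3 groups, alpha 0.05, potential group sizes 60/20/40. **Assumptions:** 5% means 5 percentage points of sleep efficiency between the extreme means, and 6.9 is a per-person SD except in step 4.

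**1. Reproducing 37.** One-way ANOVA, noncentral F, λ = Σ nᵢ(μᵢ − μ̄)² / SD². With equal groups and the third mean midway, λ = n × 25 / (2 × 47.61).

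- 37 per group: λ = 925 / 95.22 = 9.71, power 0.792. With 38 per group, power is 0.803. The large-sample chi-square approximation gives exactly 37 per group (0.803).
- 37 in total (12.33 per group): λ = 3.24, power 0.32. In the most favourable pattern (one group differs, the other two are equal) power is 0.41.

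So 37 is a near match as a number per group and far off as a total.

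**2. Overall shift comparison at attainable sizes.**

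- 60/20/40, least favourable: Groups 2 and 3 are 5 points apart and Group 1 lies at their weighted mean. λ = (20 × 40 / 60) × 25 / 47.61 = 7.00, power 0.64.
- 60/20/40, most favourable: Group 1 alone differs. λ = (60 × 60 / 120) × 25 / 47.61 = 15.75, power 0.95.
- 48/16/32 (20% loss, assumed): λ runs from 5.60 to 12.60, power 0.54 to 0.89.

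If the three groups are chronotypes, the Group 2 limit does not apply. With 120 nurses and 20% to 33% in each extreme type (assumed), power for evenly spaced means is 0.60 to 0.83.

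**3. Chronotype-specific effects (illustration only).** The documents give no chronotype shares; 20% to 33% evening types is assumed. Group 2 versus Group 3 within evening types, error df 120 − 9 = 111, half-width = 1.98 × 6.9 × √(1/a + 1/b):

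| Group 2 vs Group 3 | 95% CI half-width | Power for 5 points |
|---|---|---|
| 4 vs 8 | 8.4 | 0.22 |
| 5 vs 10 | 7.5 | 0.26 |
| 7 vs 13 | 6.4 | 0.33 |

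Power for the shift-by-chronotype test is 0.13 to 0.24 over these shares, for a 5-point effect of rotating versus day-only work that is either confined to evening types or linear across types. Larger cells do better: Group 1 versus Group 3 in intermediate types (36 vs 24, at an assumed 60% intermediate) has power 0.78 and half-width 3.6.

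**4. If 6.9 is a one-night SD averaged over the 10 days of monitoring.** SD = 6.9 × √(ICC + (1 − ICC)/10), with the intraclass correlation (ICC) assumed:

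| ICC | SD | Lowest overall power, 60/20/40 | Power, 37 in total (means evenly spaced) | Half-width, Group 2 vs 3, evening types |
|---|---|---|---|---|
| 0.1 | 3.01 | above 0.99 | 0.95 | 2.8–3.7 |
| 0.2 | 3.65 | above 0.99 | 0.84 | 3.4–4.4 |
| 0.3 | 4.20 | 0.98 | 0.72 | 3.9–5.1 |
| 0.5 | 5.12 | 0.89 | 0.54 | 4.8–6.2 |

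**The case against.** Sizing a study on a main comparison and estimating subgroup effects without powering them is common practice. The sample size paragraph does not expressly claim power for an interaction, and part of the primary objective is an overall comparison of shifts. For that comparison, 60/20/40 exceeds 0.80 under several patterns of means. All of this stands. What it does not rescue is the word guarantee, or the link to an objective framed by chronotype without a statement that the calculation leaves chronotype out.

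The meaning of 6.9 matters more. If it is a one-night SD, the overall comparison is well powered, 37 in total could be adequate at an ICC of 0.1 to 0.2, and the small-cell intervals mostly fall inside 5 points up to an ICC of 0.3. That also stands as a possibility, but the paragraph lists neither a number of nights nor an ICC, so the reader cannot rely on it.

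A repeated-measures ANOVA with 37 people each observed under three conditions comes close (0.786). It does not fit this design, in which each nurse belongs to one shift group.

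Finally, the limit of 20 in Group 2 is approximate, since the documents speak of potential participants, and it bears on the calculation only if the three groups are the shift groups.

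**Conclusion.** The point holds in two parts. That the calculation omits chronotype-specific shift effects can be read directly from the listed inputs and needs no assumption. That power above 0.80 is not guaranteed for the overall shift comparison rests on three readings: 5% as 5 points, 6.9 as a per-person SD, and the three groups as the shift groups. On those readings power is 0.64 to 0.95 with everyone enrolled and 0.54 to 0.89 after an assumed 20% loss.

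A reader might infer that the study is underpowered throughout. The documents do not support that: some patterns of means exceed 0.80 even on the per-person reading, and the one-night reading gives at least 0.89 for ICC up to 0.5. Nor do they establish that 37 must be a number per group. It is a near match on the per-person reading only, and the exact F test needs 38. The wide intervals in small chronotype cells are likewise conditional on the per-person SD and on assumed chronotype shares. On that reading a null result in evening types would not exclude 5 points; on the one-night reading this weakens or reverses.

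**What to change.** **Sample size paragraph.** Replace the guarantee with the power for the overall shift comparison at attainable group sizes (Group 2 about 20 at most, losses not replaced), given as a range over patterns of means. Name the three groups, and state whether 37 is per group or in total, whether 5% is absolute, and whether 6.9 is a per-person or a one-night SD. If it is a one-night SD, give the number of nights and the ICC. Add one sentence: this calculation does not cover shift effects within, or differing between, chronotypes.

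**Analysis paragraph.** Report the shift-by-chronotype interaction and the chronotype-specific shift contrasts with cell sizes and 95% confidence intervals. State that a non-significant result within a chronotype will not be read as absence of a shift effect.

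**Cost.** One rerun of the power calculation and some wording, with no extra enrolment, data or models. The sponsor has to retrieve the original inputs and gives up a single guaranteed figure for a less favourable range.

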Assessment of the psychological state: the POMS questionnaire identifies and quantifies affective states such as tension, depression, aggression, vigor, fatigue, and confusion. These six aspects prove to be particularly useful for assessing the subject's state of stress, fatigue and energy.

Cardiovascular risk assessment: The extent of cardiovascular risk will be calculated in all participants via QRISK2-2017 questionnaire. The questionnaire requires the inclusion of parameters such as gender, ethnicity, age, weight and height, smoking and relative frequency, the presence of diabetes, hypertension, episodes of angina, fibrillation, rheumatoid arthritis, chronic diseases in the kidney, cholesterol / HDL ratio and systolic blood pressure. The information will then be inserted into a special algorithm (<https://qrisk.org>), which will return the percentage of probability of risk involved in a cardiac problem in the next 10 years.

Evaluation of force and motor control: To evaluate the possible variations of force and motor control, the maximal voluntary isometric force (MVC) of the flexor muscles of the dominant hand fingers and their activation will be evaluated in all participants. Once the MVC has been identified, sub-maximal contractions will be required at 20, 40, 60 and 80% MVC, each lasting 20 seconds. During contraction, in addition to the force signal (model SM-2000 N, Interface, Scottsdale, UK) the surface electromyographic signal (sEMG) will be detected by the flexor muscles of the fingers. The analysis of the force signal will be evaluated (i) the ratio between the standard deviation of the force signal during the plateau phase and the mean of the signal itself (coefficient of variation, CV), as an index of stability of the muscle contraction and (ii) the distance of the force signal with respect to the target (DF) as an index of accuracy. The electromyographic signal will be analyzed in the time and frequency domain: during the maintenance period of the force plateau, the quadratic root mean (root mean square, RMS) and the mean frequency (mean frequency, MF). The temporal trend of the two signals will be used as markers of neuromuscular fatigue.

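### Sleep efficiency is compared between existing, non-randomised rosters in a model that names only shift and chronotype; no adjustment for age or sex is stated although both are collected

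*Combined protocol and SAP*

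**What the plan says.** - **Groups.** Study Design recruits nursing staff "which is subjected to three types of shift". The inclusion criterion reads "Both sexes who have a continuity of shift in the specific group of at least one year will be included in the study". No randomisation, matching or stratification is described. The available pool is about 120 staff, "of which 60 potentially belong to GROUP 1, 20 to GROUP 2 and 40 to GROUP 3".
- **Outcome.** In Statistical Analysis "the sleep efficiency was identified as the main outcome". Study Design starts actigraphy on the first day of the shift and runs it for 10 days, so there is no pre-shift value.
- **Model.** The only inferential plan is a "linear mixed ANOVA with Bonferroni correction, with a Tukey-Kramer post-hoc test", which "will be applied to estimate the effects of the work shift on the different chronotypes". Five outcome domains follow, including cardiovascular risk. No covariate, comparison of rosters at baseline or sensitivity analysis is mentioned.
- **Data in hand.** Under Clinical Evaluations, QRISK2-2017 is calculated for every participant from inputs that include "gender, ethnicity, age, weight and height, smoking and relative frequency". The only stated use of these is the risk score.
- **Existing control of confounding.** The exclusion criteria remove cardiovascular, endocrine and metabolic disease, pregnancy, and "pharmacological therapies in place that can modulate the heart rate and the quality of sleep". No age range is given.

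**The concern.** For sleep efficiency the shift main effect is a contrast between different people who came to their rosters by routes the protocol does not control. A subject random effect in a mixed model handles correlation within a person; it does nothing about who is in each roster. The exclusions, the single profession and site, and the inclusion of chronotype all help, but none of them balances age or sex.

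The primary aim is to find the shift with the least impact on staff health, and the Risk/Benefits Report says the results may inform changes to the shift system. If the day roster, say, differs in age from the 24-hour rosters, and age relates to sleep efficiency, the contrast is biased and its test rejects more often than its nominal level. The same applies to other outcomes compared between groups without a within-person time contrast. It does not apply to shift-by-time contrasts for outcomes measured twice.

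**Working it through.** **1. The plan's own figure.** Inputs from Statistical Analysis: three groups, SD 6.9, minimum detectable change 5% (read here as 5 percentage points), alpha 0.05, power above 0.80, 37 participants. With group means 0, 2.5 and 5, the noncentrality at 37 per group is λ = 37 × (2.5² + 0 + 2.5²) / 6.9² = 9.71, and power is 0.792; 38 per group gives 0.803. Read as a total (about 12 per group), 37 gives power of only about 0.32. So 37 reproduces, nearly, as a per-group number from an unadjusted three-group ANOVA. That agrees with no covariates being planned.

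**2. Bias from an omitted covariate.** Let the covariate explain a share R² of the variance and differ by D standard deviations between the control group and the other two. R² and D are assumptions; the documents give neither. Then

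bias = 6.9 × √R² × D.

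For example, 6.9 × √0.10 × 0.5 = 1.09 points.

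**3. False-positive rate of the shift test with no true shift effect.** At 60/20/40, with only the control group shifted,

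λ = (40 × 80 / 120) × bias² / 6.9² = 26.67 × R² × D²,

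referred to a noncentral F with 2 and 117 degrees of freedom. The plan does not say what the Bonferroni correction covers, so three levels are shown: 0.05, 0.0167 (three comparisons) and 0.01 (five domains).

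| R² | D | Bias (points) | λ | α 0.05 | α 0.0167 | α 0.01 |
|---|---|---|---|---|---|---|
| 0.01 | 0.25 | 0.17 | 0.017 | 0.051 | 0.017 | 0.010 |
| 0.05 | 0.5 | 0.77 | 0.333 | 0.075 | 0.029 | 0.018 |
| 0.10 | 0.5 | 1.09 | 0.667 | 0.102 | 0.042 | 0.028 |
| 0.10 | 1 | 2.18 | 2.667 | 0.283 | 0.154 | 0.115 |
| 0.20 | 1 | 3.09 | 5.333 | 0.520 | 0.348 | 0.282 |

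If Group 2 is the one that differs, the rates at 0.05 are 0.051, 0.066, 0.082, 0.190 and 0.345.

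**4. Chronotype in the model.** This was simulated with 6,000 replicates, an assumed 20/60/20% chronotype split and chronotype R² of 0.05. For the five cases at 0.05 the shift test rejects in 0.052, 0.077, 0.110, 0.285 and 0.542. Adding age and sex returns it to 0.053, 0.051, 0.051, 0.050 and 0.044. The Tukey-Kramer familywise rate is 0.050 to 0.530 unadjusted and 0.045 to 0.051 adjusted.

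**5. Shift-by-chronotype term added** (5,000 replicates). The shift main effect rejects in 0.052 to 0.444 unadjusted and 0.043 to 0.050 adjusted. The interaction test stays at 0.043 to 0.052 even without adjustment, because the imbalance was set equal in every chronotype.

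**6. What adjustment cannot do.** Add an unmeasured factor (R² 0.05, D 0.5) to the middle case (R² 0.10, D 0.5). Unadjusted bias is 1.09 + 0.77 = 1.86 points. With age and sex in the model the simulated bias is 0.76 points, and the rejection rate falls from 0.222 to 0.079.

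**The case against.** - **The sample may be smaller.** The 60/20/40 split is the potential pool, not a planned enrolment, and 37 is not labelled as per group or total. This stands as a limit on the rates. For the lowest, middle and highest cases they are 0.051, 0.098 and 0.486 at 37 per group, and 0.050, 0.065 and 0.183 if 37 is the total (split 18/6/13). The bias in points does not depend on the sample size.
- **The inputs are assumed.** This stands. The range starts where there is no visible harm, and its top case (R² 0.20, 1 SD) is demanding for one profession at one site with relevant disease and drugs excluded.
- **The question is about chronotype.** The aim is framed by chronotype, and the interaction test keeps its level if imbalance is the same across chronotypes. But naming the least harmful shift needs a shift contrast, overall or within chronotype, and that stays open to confounding.
- **Silence is not exclusion.** The section omits covariates; it does not rule them out. This is so, but it leaves them to be chosen after the data are seen.
- **Ten days of actigraphy could give a within-person contrast.** The plan states none for sleep efficiency, and the shift main effect would still be between persons.
- **Why only age and sex?** Physical activity (IPAQ), smoking, weight and height are also collected. The choice of age and sex is a minimum, and others could be argued for.

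**Conclusion.** The concern holds. Followed as written, the plan gives a shift contrast for sleep efficiency that is open to confounding by age and sex, although both are recorded for everyone. That gap is certain; its size is not, because the documents report no age or sex mix and no relation of either to sleep efficiency.

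The illustrated bias is 3% to 62% of the 5-point target (0.17/5 to 3.09/5). A stricter Bonferroni level lowers the false-positive rates in absolute terms, but in the middle and upper cases they stay above their own nominal level. The results assume no true shift effect, SD 6.9 and one imbalanced covariate. The return to nominal level after adjustment assumes that nothing else differs between rosters. The point should be corrected before analysis.

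**What to change.** Add to Statistical Analysis, in substance:

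> The primary model for sleep efficiency, and for other outcomes compared between groups without a within-person time contrast, will include age (continuous) and sex as fixed effects in addition to shift and chronotype. Unadjusted results will be shown beside adjusted results.

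Word conclusions as associations with roster, and state that unmeasured selection into or out of rosters remains. An unadjusted group difference in QRISK2 should not be read as a shift effect, since age and sex enter the score itself.

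**Cost.** A few sentences, no new data, and about two degrees of freedom.

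- *Balanced covariates that explain nothing:* at 60/20/40 with chronotype in the model, error degrees of freedom go from 115 to 113. Power goes from 0.8928 to 0.8926 (means for Groups 1, 2, 3 of 0/2.5/5) or from 0.6716 to 0.6714 (2.5/0/5).
- *Imbalanced covariate that explains nothing:* the standard error of control versus Group 1 is multiplied by √[(1/40 + 1/60 + D²/117) / (1/40 + 1/60)], which is 1.025 at D = 0.5 and 1.098 at D = 1. With chronotype and sex also in the model, simulation gives 1.034 and 1.109. The largest simulated power loss is from 0.71 to 0.62 (means 2.5/0/5, D = 1).
- *Balanced covariates that explain 10% of variance:* power rises, for example from 0.792 to 0.835 at 37 per group.
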